# 3 Objective of the study

To investigate whether intralaesional injection with collagenase clostridium histolyticum (XiapexR) into the stricture followed by dilation 24 hours later improves the outcome of patients with refractory gastrointestinal strictures as compared to dilation alone (standard of care).

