# 4 End point(s) and timepoint(s) of evaluation

### Primary outcome measure:

Number of repeat dilations that are required over a timespan of 6 months.

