### Secondary outcome measures:

1) time to first repeat dilation

- 2) complication rate.
- 3) For upper gastrointestinal strictures only: Dysphagia/gastric outlet obstruction

score (0:, able to eat normal diet; 1: moderate passage: able to eat some solid foods;

2: poor passage: able to eat semi-solid foods only; 3: very poor passage: able to drink liquids only; 4: no oral intake possible

4) For lower gastrointestinal strictures only: (Ileo)colorectal obstruction scoring system (0, requiring continuous decompression; 1, no oral intake; 2, liquid or enteral nutrition; 3, oral intake of soft solids, low-residue diet, or full diet with symptoms of stricture\*; and 4, oral intake of soft solids, low-residue diet, or full diet without symptoms of stricture\*. Symptoms of stricture include abdominal pain/cramps, abdominal distension, nausea, vomiting, constipation, and diarrhea which are related to gastrointestinal transit).

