## 7.3 The subjects

### 7.3.1 Number of subjects

Active group: 10 patients presenting with refractory GI strictures.

Control group: A historical cohort that consists of 40 consecutive patients that received an endoscopic balloon dilation 12-15mm for a refractory GI stricture at our centre.

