# 8 Procedures

## 8.1 Procedures

After informed consent, patients with an a refractory upper GI stricture will receive a first esophagogastroscopy or ileocolonoscopy with local injection of XiapexR injection into the stricture prior to dilatation. One vial (0.9mg) xiapex in 3ml dissolvent (also provided by the company) will be divided over 4 quadrants within the fibrotic stricture. After 24 hours, a second esophagogastroscopy or ileocolonoscopy will be performed to perform balloon dilation of the stricture 12-15mm (standard of care). The historical cohort will not undergo any procedures, but their patient file will be reviewed to gain outcome data. ICF will be obtained if the patient is still in follow-up at our department.

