## 8.2 Flowchart

- Between day -7 to day -1: Informed consent

- Day 0: Endoscopy, xiapex injection into the strictures (4 quadrants, 0.75ml or 0.25mg per quadrant)
- Day +1: Endoscopy, CRE balloon dilation 12mm to max 15mm
- Day +2 to month 2: clinical evaluation (by phone) every 2 weeks with a window of 3 days (see above for primary and secondary outcome measures)
- Month 2-month 6: Clinical evaluation (by phone) every 4 weeks with a window of 3 days (see above for primary and secondary outcome measures)

The expected total duration of the trial is 18 months.

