### Adverse events (AE)

The following information will be recorded:

- nature of adverse event
- date and time of occurrence and disappearance
- intensity: mild, moderate or severe
- frequency: once, continuous or intermittent
- decision regarding study: continuation or withdrawal
- relation to the study medication (see below)

AE's will be recorded from the first drug administration until the end of the trial. Special attention will be given to those subjects who have discontinued the trial for an AE, or who experienced a severe or a serious AE.

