## 12.3 Statistical analysis

This is a proof of concept open label study that will compare outcome data with a historical control group. Only descriptive analyses will be performed, the sample size will be too low for any meaningful statistical analysis.

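### Active outcomes come from scheduled calls and prospective adverse event recording, control outcomes from file review only, and the plan compares them without a common source or definition

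*Combined protocol and SAP*

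**What the plan says.** The primary outcome (section 4) is "Number of repeat dilations that are required over a timespan of 6 months". The secondary outcomes include time to first repeat dilation, symptom scores and the "complication rate", which is named without a definition or a data source.

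The two groups reach these outcomes by different routes.

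- **Active group (10 patients).** The flowchart in section 8.2 sets "Day +2 to month 2: clinical evaluation (by phone) every 2 weeks with a window of 3 days", then four-weekly calls to month 6, and ties both series to the primary and secondary outcomes. Section 11 adds that "AE's will be recorded from the first drug administration until the end of the trial", graded from mild to severe. It places these events in both the patient's file and the CRF. Section 13 describes data collection as prospective.
- **Control group (40 historical patients, same centre).** Section 8.1 states: "The historical cohort will not undergo any procedures, but their patient file will be reviewed to gain outcome data". Consent is sought only from those who still attend the department, so the plan accepts that some may have left.

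Section 12.3 then brings the groups together: "This is a proof of concept open label study that will compare outcome data with a historical control group". It limits the analysis to description.

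**The concern.** A difference between the groups can arise because events are looked for harder in one of them. Active patients are asked about their outcomes on a schedule. A control contributes only what was written down in routine care at this centre, for as long as the patient kept attending.

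Two results are exposed. The complication rate is the only safety measure among the listed outcomes, and section 7.3.6 says it is unknown whether the injection raises the perforation risk. The number of repeat dilations is the primary outcome, and a benefit could be partly hidden if control dilations are undercounted. Because no test is planned, readers will rely on the side-by-side figures, so these need to measure the same thing.

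**Working it through.** The plan gives no event rate, effect size or capture rate, so there is no figure of its own to reproduce. The check sets the sections side by side and then illustrates the size.

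**Contacts.** Two-weekly calls to month 2 fall at about weeks 2, 4, 6 and 8. Four-weekly calls to month 6 fall at about weeks 12, 16, 20 and 24. That is 4 + 4 = 8 outcome contacts per active patient and none per control.

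**Harmonisation.** No section gives a shared definition of a complication, a common abstraction form, a minimum control follow-up, or a way to find dilations done elsewhere.

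**Which outcomes are exposed**

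- *Complications:* mild or moderate events reach a control's file only if someone noted them in routine care. Severe events such as perforation would normally be in the file of either group.
- *Repeat dilations and time to the first:* these are procedures with endoscopy reports, and controls were treated at the same centre. What remains is off-site dilations and controls who stopped attending. The consent sentence in section 8.1 shows that some controls may have left, not that they left within 6 months. Separately, a scheduled call may itself prompt a dilation in the active group.
- *Symptom scores:* the active scores come from the calls, and controls have no equivalent.

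**Illustrative size.** Let s be the share of control events that file review captures, and assume complete capture in the active group. Then observed active/control ratio = true ratio / s. The values of s are assumptions.

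| s | no true difference (1/s) | true 30% reduction (0.70/s) |
|---|---|---|
| 0.9 | 1.11 | 0.78 |
| 0.8 | 1.25 | 0.875 |
| 0.7 | 1.43 | 1.00 |
| 0.6 | 1.67 | 1.17 |

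At s = 0.7 a true 30% reduction in dilations would look like no effect. For complications, with an assumed true risk of 10% in both groups, expected recorded control events are 40 × 0.10 × s: 4.0 with full capture, 3.6 at s = 0.9 and 2.0 at s = 0.5. The chance of at least one event among 10 active patients is 1 − 0.9^10 = 65%.

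**Against sampling error.** Assume Poisson counts with a mean of m dilations per patient. The standard error of the log ratio is √(1/(10m) + 1/(40m)). For m = 2 it is √(1/20 + 1/80) = 0.25, a 95% factor of exp(1.96 × 0.25) = 1.63. For m = 4 it is √(1/40 + 1/160) = 0.177, a factor of 1.41. Distortions of 1.11 to 1.25 lie inside that noise. Unlike the noise, they push in a consistent direction.

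**The case against.** The strongest reply is that this is a small, openly descriptive pilot. Dilations at the same centre will be in the file, and any undercount in controls works against the drug, so a favourable result would survive it. Much of this stands. It makes the primary outcome the less affected one, and the capture shares above show what could happen, not what will. It does not remove the problem, because section 12.3 drops formal testing but keeps the comparison.

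A reader might also draw four stronger conclusions that the documents do not support.

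- *That every adverse event counts as a complication, so that a mild complaint scores in one group only.* The term is undefined, and section 11 does not link adverse events to that outcome. The complication that section 7.3.6 discusses at most length is perforation.
- *That post-injection complaints are missed in controls.* Controls had no injection, so such events cannot occur in them. An excess of this kind would be a real treatment effect.
- *That the comparison will overstate harm, or that neither outcome can say anything about the drug.* Missed control events tend to act against the active treatment, but the size is unknown. Unblinded decisions to dilate could act either way, so the net direction is not fixed.
- *That using the patient file for both groups is enough.* Section 11 puts trial-recorded adverse events into the active patients' files, so those files are richer. The type of event must be restricted as well.

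**Conclusion.** The point holds: the groups are measured by different means, they are compared, and nothing in the plan aligns them. The effect is probably largest for the undefined complication rate and smaller for repeat dilations and time to the first. If files miss control events, the bias tends to run against the active treatment. Its size cannot be derived from the documents. The ratios of 1.11 to 1.67 rest on assumed control capture of 90% to 60%, complete active capture and no true difference. Historical controls are a legitimate choice for a pilot, and unlike data sources do not follow from that choice, because the centre holds a file for both groups. The plan should be changed, but the point does not call the study itself into question.

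**What to change.** Amend sections 8.1 and 12.3 as follows.

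1. Take the compared repeat dilations, time to first repeat dilation and complications for both groups from the centre's endoscopy reports and routine patient file, using one abstraction form and one definition.
2. Limit the compared complications to events that routine care would document whether or not the patient was in a trial, for example confirmed perforation, bleeding needing intervention, or unplanned admission.
3. Count dilations over 6 months from the index dilation in both groups.
4. Count complications from the Day 0 injection in the active group and from the index dilation in controls. A clock that started at dilation in both groups would drop events in the 24 hours between injection and dilation, the period most specific to the drug.
5. State in advance what counts as complete 6-month file follow-up, and report how many controls have it. Repeat the comparison in those controls, so that a patient lost to the centre is not counted as having had no dilations.
6. Report call-only events, minor adverse events and phone-based symptom scores as active-group-only results.

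The cost is protocol wording and the control form applied to 10 more files. Treatment, visits and sample size do not change. The comparative table will omit minor and off-site active-group events, which are still reported separately. Dilations prompted by the scheduled calls will still be counted and should be stated as a limitation.

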## 8.2 Flowchart

- Between day -7 to day -1: Informed consent

- Day 0: Endoscopy, xiapex injection into the strictures (4 quadrants, 0.75ml or 0.25mg per quadrant)
- Day +1: Endoscopy, CRE balloon dilation 12mm to max 15mm
- Day +2 to month 2: clinical evaluation (by phone) every 2 weeks with a window of 3 days (see above for primary and secondary outcome measures)
- Month 2-month 6: Clinical evaluation (by phone) every 4 weeks with a window of 3 days (see above for primary and secondary outcome measures)

The expected total duration of the trial is 18 months.

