# 6 Introduction

The main causes of benign gastrointestinal (GI) strictures are inflammatory (eg: reflux disease, eosinophilic esophagitis, Crohn's disease, caustic...) or iatrogenic (postirradiation, post endoscopic (sub)mucosal resection, post radiofrequency ablation, anastomotic...). Most strictures respond well to endoscopic balloon dilation. Nonetheless, more than one third of patients develop recurrent symptoms after dilation within the first year (1).

In some case, the stricture can be difficult to treat and require multiple dilation sessions to obtain long-term relief of dysphagia, eating difficulties or lower GI obstructive symptoms (2, 3). A refractory stricture is defined as a cicatricial or fibrotic narrowing luminal diameter resulting in clinical symptoms of a) dysphagia (esophageal strictures), b) gastric outlet obstruction (for strictures of the stomach, pylorus, duodenum of gastrojejunal anastomosis) or c) lower GI obstruction (abdominal distension and cramps, vomiting) with an inability to successfully remediate the anatomic problem to a sufficient diameter over 3 dilation sessions at two-week intervals (4). A recurrent stricture is defined as a cicatricial or fibrotic narrowing with an inability to maintain a satisfactory luminal diameter for four weeks (4). Several options (stenting, intralesional injection of corticosteroids, needle knife incision) have been proposed to manage these strictures, with a varying success rate (5). A significant proportion of patients will finally need self-bougienage or surgery (5).

In conclusion, the treatment of GI strictures remains a challenge for clinicians and there is an unmet need for novel approaches to manage the patients suffering from this condition in order to avoid repeated dilations and/or invasive surgery.

XiapexR is a locally injectable collagenase approved for the management of Dupuytren's and Peyronie's disease (6, 7). Xiapex is a mixture of two collagenases, enzymes produced by the bacterium *Clostridium histolyticum* that dismantle collagen. Approximately 24 hours after local injection, the collagen fibres have lost their

strength and can be easily broken by manipulation. This therapy has been a breakthrough in the management of Dupuytren's disease, avoiding surgery in the vast majority of patients (6).

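### No symptom score is scheduled before treatment, so change from the pre-treatment state on the two obstruction scores cannot be calculated from the planned data

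*Combined protocol and SAP*

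**What the plan says.** Section 3 sets out to learn whether the injection followed by dilation "improves the outcome of patients with refractory gastrointestinal strictures as compared to dilation alone". Section 4 includes two symptom scales among the secondary outcomes: "For upper gastrointestinal strictures only: Dysphagia/gastric outlet obstruction" score, running from 0 (best) to 4 (worst), and "For lower gastrointestinal strictures only: (Ileo)colorectal obstruction scoring system", running from 0 (worst) to 4 (best). Neither entry gives an assessment time, a baseline or a definition of change.

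Section 8.2 is the only assessment schedule. Its single entry before treatment is "Between day -7 to day -1: Informed consent". Day 0 is endoscopy with injection, and Day +1 is endoscopy with dilation. The pointer to the primary and secondary outcomes appears only on the two phone-contact rows: "Day +2 to month 2: clinical evaluation (by phone) every 2 weeks with a window of 3 days", and from month 2 to month 6, "Clinical evaluation (by phone) every 4 weeks with a window of 3 days".

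The comparator in section 7.3.1 is "A historical cohort that consists of 40 consecutive patients", whose outcome data come from file review (section 8.1). Section 12.3 limits the analysis to description.

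**The concern.** A symptom score taken only after treatment shows where a patient ended, not how far the patient moved. The objective is about improvement, and these two scores are the only planned measures of how well patients can eat or how obstructed they are. Without a starting value, the same follow-up level may mean no change or a large one.

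The comparison with controls has the same weakness. The groups are not randomised, so a gap in follow-up scores between 10 treated patients and 40 historical controls may reflect only who started worse. As a hypothetical example on the upper scale, a treated patient going from 2 to 1 and a control going from 3 to 2 have each gained one level, yet their follow-up scores differ by one level.

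The loss is permanent. Once a patient has been injected, only recall or routine clinical notes remain.

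**Working it through.** The protocol states no figure to reproduce here. The check is a count of scheduled assessments, a search for another source of a starting score, and a small calculation of what a follow-up score alone can mean.

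**1. Assessments per treated patient (section 8.2, assuming no missed calls)**

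| Period | Content | Scores scheduled |
|---|---|---|
| Day -7 to -1 | consent | 0 |
| Day 0 | endoscopy, injection | 0 |
| Day +1 | endoscopy, dilation | 0 |
| Day +2 to month 2, every 2 weeks | phone contact, about weeks 2, 4, 6, 8 | about 4 |
| Month 2 to month 6, every 4 weeks | phone contact, about weeks 12, 16, 20, 24 | about 4 |

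After treatment: 4 + 4 = about 8 per patient; 8 × 10 = about 80 in the active group. Before treatment: 0 per patient; 0 × 10 = 0. The count after treatment depends a little on how the boundary contacts are read. The count before treatment does not.

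**2. Could another section supply a starting score?**

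- Section 4 (secondary outcomes): names the scales and their levels, with no timing.
- Section 6: describes a refractory stricture as a "cicatricial or fibrotic narrowing luminal diameter resulting in clinical symptoms". This implies some symptoms but fixes no level.
- Section 7.3.1: calls the active patients refractory, again without a level.
- Section 7.3.2: requires a stricture and a recent previous dilation. It requires neither the section 6 definition nor a score.
- Section 8.1: control files are reviewed for outcome data; no pre-dilation score is named.
- Section 11: the CRF record between consent and first dose covers medical events, not these scales.
- Section 12.3: mentions no baseline.

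None does.

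**3. What a follow-up score alone can mean**

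Assume that every patient starts with symptoms: upper start *s* = 1 to 4, lower start *s* = 0 to 3 (level 4 on the lower scale is symptom-free). Let *f* be the follow-up score. Levels gained are *s* − *f* on the upper scale and *f* − *s* on the lower.

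| Upper *f* | Range of *s* − *f* | Lower *f* | Range of *f* − *s* |
|---|---|---|---|
| 0 | 1 to 4 | 4 | 1 to 4 |
| 1 | 0 to 3 | 3 | 0 to 3 |
| 2 | −1 to 2 | 2 | −1 to 2 |
| 3 | −2 to 1 | 1 | −2 to 1 |
| 4 | −3 to 0 | 0 | −3 to 0 |

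Each follow-up score leaves a span of 3 levels on a scale of 0 to 4. At the best score, improvement is certain but its size is not. At middle scores, even the direction is open.

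**The case against.** The strongest reply is that the plan never promises change scores. Section 4 names the scores as outcomes, section 12.3 plans description only, and the objective is a contrast with dilation alone, carried mainly by the number of repeat dilations. That is right as far as it goes: this is a gap, not a contradiction, and follow-up levels can be described.

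A second reply is that lack of comparability with historical controls affects every outcome, so a starting score is only a partial answer. This also stands. The score would show imbalance but not remove it, and no adjustment is planned. The control files may lack these scores at follow-up as well as before dilation. The primary outcome and time to first repeat dilation are unaffected only in the sense that they can be computed without a symptom score.

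Third, the missing information might be recovered. Treated patients had a dilation within the previous 3 months, the scales are largely simple intake categories, and the CRF is not among the documents and might hold a baseline field. These are possibilities; no section plans to capture the score.

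Finally, the ambiguity about direction disappears at the best score if all patients start with symptoms, and the study is small and exploratory. These points limit the weight of the concern. They do not supply the missing value, and describing change in even one patient needs it.

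**Conclusion.** The concern holds. As scheduled, 0 of the 10 treated patients would have a planned pre-treatment score, against about 8 scores each afterwards, so change from the pre-treatment state on secondary outcomes 3 and 4 cannot be calculated from the planned data. Nor could the report describe whether treated patients and controls started at similar severity on these scales.

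The count of 8 assumes no missed calls, and the ranges of levels gained assume a symptomatic start. The finding of zero scores before treatment needs neither assumption. It rests on the documents available, without sight of the CRF. The consequence is confined to two secondary outcomes, each applying to part of the group. It should be corrected, but it does not prevent the main results from being reported.

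**What to change.** Add to section 8.2 one recording of the applicable score, with the stricture site, after consent and before the Day 0 injection. State in section 12.3 that baseline, follow-up and change will be listed per patient and described separately for the two scales, because they run in opposite directions. For controls, abstract a pre-dilation score only where the file documents it, and report how many of the 40 have one. Any baseline difference between the groups should be presented as a description of imbalance, not as an adjustment for it.

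The cost is one CRF item per treated patient (10 entries) at an existing contact, and one item in the review of up to 40 files already planned. No visit or procedure is added. The main limitation is that control scores may be incomplete. The change needs to be made before the first patient is injected; for anyone already treated, a score taken from clinical notes should be labelled as retrospective.

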## 7.2.8 Known side effects of the medication

After local injection the collagenases do not reach the bloodstream in significant amounts and are presumed to largely stay at the point of injection until they are broken down by proteases. As a result, side effects are uncommon and are most often injection site reactions including lymphadenopathy (swollen lymph nodes), itching, pain, oedema, and bleeding (for example in the form of bruises or ecchymoses). Allergic reactions are seen in less than 1% of patients Drug accountability

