### 7.3.6 Possible advantages and risks for the subjects

It is possible that participation to the study will result in less need for repeat dilations for a refractory upper GI stricture (unknown).

Every dilation carries the risk of perforation, even in the most experiences hands. No additional dilations are performed in light of the study. It is unknown whether local injection of the study drug augments the risks of perforation. Every patient is carefully monitored after dilation (standard of care). Upon clinical suspicion of perforation, a CT scan is performed for confirmation.

suspicion of perforation, a CT scan is performed for confirmation. In case of confirmed perforation, endoscopic stenting is immediately performed to bridge the defect, allowing healing of the defect. The stent can most of the time be removed after 6 weeks. In some case, endoscopic clipping is the treatment of choice to close the iatrogenic perforation. Surgical intervention is seldomly needed

Side effects of the study drug (XiapexR) are expected to be very limited, as the study drug does not enter the bloodstream in significant amounts and is rapidly degraded in the bloodstream by proteases. Local reactions (bleeding, swelling, inflammation) are theoretically possible. Like all foreign substances, Xiapex can induce allergic reactions but these seem to be very rare (only 1 case described in literature).

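### Section 8.2 plans no contact for at least Day +6 to Day +10, so mild reactions that start after the first days would be dated from recall, and an early re-dilation may come before any symptom score

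*Combined protocol and SAP*

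**What the plan says.** Section 8.2 sets out two in-person visits: "Day 0: Endoscopy, xiapex injection into the strictures" and "Day +1: Endoscopy, CRE balloon dilation 12mm to max 15mm". After these, all planned contact is by telephone: "Day +2 to month 2: clinical evaluation (by phone) every 2 weeks with a window of 3 days", and then "Month 2-month 6: Clinical evaluation (by phone) every 4 weeks with a window of 3 days". The flowchart ties these calls to the primary and secondary outcome measures, so they are the stated means of collecting the symptom scores (secondary outcomes 3 and 4 in section 4).

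Section 11 asks for several details of each adverse event, among them "date and time of occurrence and disappearance", intensity and frequency. It sets the recording period, from first dose to the end of the trial, but no contact days.

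On what might be seen, section 7.2.8 says that "side effects are uncommon and are most often injection site reactions including lymphadenopathy (swollen lymph nodes), itching, pain, oedema, and bleeding". Section 7.3.6 says "It is unknown whether local injection of the study drug augments the risks of perforation", and adds that patients are monitored after dilation as standard of care, without giving a duration. Section 6 states that the drug has not been evaluated in refractory GI strictures.

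**The concern.** The flowchart line can be read in two ways. The first call is either on Day +2 or two weeks after treatment starts. On both readings, part of the first two weeks has no planned contact.

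Two things are at stake. The first is the dating and grading of mild reactions. Complication rate is a named secondary outcome, and there are 10 active patients (section 7.3.1), so one patient with a missed event moves that group's rate by 1/10, or 10 percentage points. A call made well after a short-lived reaction can obtain its onset, end and intensity only from memory.

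The second is the symptom score in patients who do badly early. If the first score is taken about two weeks on, a patient who needs another dilation by then may have no score that describes the period after the study dilation. Later scores would reflect the second dilation as well.

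**Working it through.** The plan states no figure on this point, so there is none to reproduce. The check is calendar arithmetic.

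**Inputs**
- From section 8.2: injection on Day 0, dilation on Day +1, calls 14 days apart up to month 2, window of 3 days.
- Assumption: the window means plus or minus 3 days. The plan gives no direction.
- Assumption, for step 4 only: a repeat dilation 14 days after the study dilation, on Day 1 + 14 = Day 15. The interval is borrowed from the definition of a refractory stricture in section 6 ("over 3 dilation sessions at two-week intervals"). It is not a planned schedule.

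**Step 1. First call on Day +2**
- Latest first call: 2 + 3 = Day 5. The line itself starts at Day +2, so the call falls on Day 2 to 5.
- Second call: 2 + 14 = Day 16, with window 16 ± 3 = Day 13 to 19.
- Days with no planned contact whatever day is used: Day 6 to Day 12, which is 7 days.
- Longest permitted interval between the two calls: 19 − 2 = 17 days.

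**Step 2. First call two weeks on**

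| 14 days counted from | Nominal day | Window (± 3) | Days after dilation (day − 1) |
|---|---|---|---|
| Day 0 | 14 | 11–17 | 10–16 |
| Day +1 | 15 | 12–18 | 11–17 |
| Day +2 | 16 | 13–19 | 12–18 |

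The first planned contact after dilation is therefore on some day from Day 11 to Day 19, 10 to 18 days after it.

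**Step 3. What both readings share**
- Neither plans a contact from Day 6 to Day 10.
- Plus or minus 3 days is the generous reading. If the window is 3 days in total (± 1), the gap in step 1 runs from Day 4 to Day 14 (latest first call 2 + 1 = 3, earliest second call 16 − 1 = 15). The first call in step 2 then falls on Day 13 to 17.

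**Step 4. Can a score come before an early re-dilation?**
- First call on Day +2: yes. A score from Day 2 to 5 exists before Day 15.
- First call two weeks on: Day 15 lies inside all three windows, so the call may come before or after it. The window days before Day 15 number 4 (11–14), 3 (12–14) and 2 (13–14) out of 7. If every call day in the window were equally likely, the chance of no prior score would be 3/7 = 43%, 4/7 = 57% or 5/7 = 71%.
- With re-dilation at four weeks instead (1 + 28 = Day 29), the first call is on Day 19 at the latest, so the chance is 0%.

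The result depends on when re-dilation occurs, and the documents do not say. The percentages show this dependence and do not estimate what would happen in the trial.

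**The case against.** The strongest reply is that early safety does not rest on the telephone calls alone, and this stands in large part. The patient is seen at the Day +1 endoscopy, about 24 hours after injection. Section 7.3.6 provides for monitoring after dilation. Serious events have their own reporting route in section 11, and every patient carries a card with a 24-hour emergency number. These safeguards do not cover mild events later in the gap: the monitoring has no stated length, and the number works only if the patient decides to call.

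A reader might infer more than the documents support:
- **That all early reactions are taken from recall.** Those of the first 24 hours can be observed directly, and a Day +2 call would come one day after dilation.
- **That no useful symptom score exists on either reading.** A Day +2 call gives a post-dilation score. Dismissing it as too early is a judgement that the documents do not make.
- **That the first call could be valid before injection** (2 − 3 = Day −1). The line's own lower bound is Day +2.
- **That 43–71% of early failures would lack a score.** This needs a Day 15 re-dilation. Section 7.3.2 requires only one dilation in the previous three months, so patients need not be on a two-week cycle.
- **That reactions are known to cluster in the gap.** Sections 7.2.8 and 7.3.6 give no time course.

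A further objection is that the controls come from file review (section 8.1), so extra solicited calls in the active group widen the difference in how events are found. That is a fair cost, and the reporting has to deal with it. Nor would extra calls supply a baseline score, which the flowchart does not list. The early scores would describe patients' state after dilation, not change from before treatment.

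**Conclusion.** The point holds in a limited form. Section 8.2 leaves the day of the first call and the direction of its window unstated. On the plus or minus 3 day reading, the gap is Day +6 to Day +12 if calls start on Day +2. If they start two weeks on, it runs from after the Day +1 dilation until Day 11–19. Fixing the start day alone would not close it, since both readings leave Day 6 to Day 10 without planned contact.

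The consequence is confined to mild, non-serious reactions starting after the first days and, if calls start two weeks on, to the outcome 3 or 4 scores of patients re-dilated by about Day 15. How many patients that would be cannot be derived from the documents. The number of repeat dilations and the time to the first one are dated procedures and are untouched. This is an inexpensive improvement to secondary data in a descriptive pilot (section 12.3). It does not threaten the primary outcome.

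**What to change.** In section 8.2:
- Add two short data-collection calls in the first two weeks, for example about Day +3 and Day +8, with narrow windows that cannot fall before Day +2. Each records adverse events and the outcome 3 or 4 score.
- State the day on which the two-weekly series starts, the direction of the 3-day window, and that this window applies only to the two-weekly and four-weekly calls.

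In section 12.3:
- Report the last symptom score before the first repeat dilation.
- Report adverse events by time of onset.
- Limit the complication comparison with the historical cohort to events that a patient file would also capture. Report mild events solicited by call for the active group only.

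The cost is 2 calls × 10 patients = 20 short calls, plus a few lines of text. The downside is that more mild events will be solicited in the active group than in the file-review controls, which the last reporting rule is meant to contain. Patient care does not change.
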